	
replaced in the Monotherapy period, in Cycle 1 or 2, the number of patients will be higher than 34.
 
Analysis sets:
 
There will be two analysis sets
 
• Safety Set: All patients treated with at least one dose of idronoxil will be included in the Safety Set (SS). All analyses of safety, toxicity, and PK will be performed for this set.• Full Analysis Set (FAS): All patients who completed at least one cycle of combination therapy (at any NOX66 dose). 
Analyses of efficacy, tolerability, and biomarkers will be performed for the FAS. Separate summaries may be provided for patients participating in the Dose Escalation and Dose Expansion parts.
 
Safety (Primary analysis):
 
The safety profile will be based on Serious Adverse Events (SAEs), Treatment Emergent Adverse Events (TEAEs), standard clinical laboratory parameters (clinical chemistry, hematology, urinalysis), vital signs measurements, ECG parameters, and physical examination findings.
 
Adverse events (AE) will be coded using the Medical Dictionary for Regulatory Activities and summarized by dose when NOX66 is given alone or in combination with doxorubicin. The number and percentage of patients reporting TEAEs will be calculated overall, by system organ class, and by preferred term for each dose level. Adverse events will also be graded for severity according to the National Cancer Institute Common Terminology Criteria for Adverse Events, Version 5.0.
 
Serious Adverse Events (SAEs) will be summarized separately.
 
Cardiac AEs (including clinically significant abnormalities in ECG rhythm and waveform morphology reported as TEAEs) and changes in echocardiographic parameters will be summarized.
 
Descriptive statistics will be provided for demographics, baseline characteristics, and exposure to treatment by cohort.
 
Univariate summary statistics will be provided by dose group at each visit for quantitative laboratory parameters and vital signs and for the change from baseline in these parameters. For laboratory values and vital signs with defined CTC grades, shift tables will be provided for CTC grades from baseline to end of study and from baseline to worst value on study.
 
Univariate summary statistics will be presented for ECG parameters for the value at each measurement time point and the change from baseline to each measurement time point. A similar analysis will be provided for the worst value of each ECG parameter on study.
 
Findings from physical examinations and ECOG performance status will be summarized by dose of NOX66 given alone or in combination with doxorubicin.
 
Pharmacokinetics (Secondary analysis):
 
Individual blood concentration-time data and blood PK parameters will be summarized using descriptive statistics by dose and sampling time for idronoxil and metabolites. Separate summaries will be provided for PK

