7 STUDY OBJECTIVES

7.1 PRIMARY OBJECTIVES

- To estimate the maximum tolerated dose (MTD) of NOX66 in combination with doxorubicin
- To characterize the safety and tolerability of NOX66 alone and in combination with doxorubicin.

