8.1.1 DOSE-ESCALATION

For all dose escalation cohorts, there will be 7 days of monotherapy treatment with NOX66 followed by a 5- day washout period prior to the start of combination cycles of NOX66 and doxorubicin. The purpose of the monotherapy treatment is to evaluate the safety and tolerability of NOX66 when administered alone and as well as single and multiple dose PK of idronoxil.

The dose-escalation part of the study will include three planned Treatment Groups (800, 1200, 1800 mg daily) of 3 patients each. The first 3 patients will be entered at Dose Level 1 and will receive daily doses of NOX66 for 7 days. All of these doses, except for the 1800 mg have been evaluated in 2 previous clinical trials and have been relatively well tolerated as monotherapy for 14 days and in combination with carboplatin for 42 days.

After a rest period of 5 days and if no significant toxicities (DLT equivalent toxicity) have occurred, patients will enter the combination therapy part of the study which will consist of up to 6 x 21-day treatment cycles. Each cycle will consist of 7 days of NOX66 (at the assigned dose), doxorubicin (75 mg/m²) on Day 2 of the 21-day cycle (administered at approximately 1 hour after rectal application of NOX66) and a rest period of 2 weeks.

For the 800 mg and 1200 mg dose levels NOX66 will be administered twice-daily (BID) with a 400 mg or 600 mg suppository, respectively, and the 1800 mg dose level will entail administration of a 600 mg suppository three times daily (TID). In all cohorts, doxorubicin will be given initially at 75 mg/m² as an intravenous infusion over 15 minutes (or as per standard of care). This dose may be reduced to 60 mg/m², at the Investigator's discretion for unacceptable Grade ≥ 2 toxicity. A dose reduction of 50% is recommended if serum bilirubin is 1.2 -3.0 mg/dL prior to a cycle. If serum bilirubin is 3.1-5.0 mg/dL prior to a cycle, a 75% dose reduction of doxorubicin is recommended.

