14.2 ANALYSIS SETS

There will be two analysis sets

- Safety Set: All patients treated with at least one dose of idronoxil will be included in the Safety Set (SS). All analyses of safety, toxicity, and PK will be performed for this set.
- Full Analysis Set: All patients who complete at least one cycle of idronoxil + doxorubicin combination therapy will be included in the Full Analysis Set (FAS). Analyses of efficacy, tolerability, and biomarkers will be performed for this set.

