14.3.11 QUALITY OF LIFE

All Quality of Life (QoL) analyses will be performed on the FAS. Scales from the EORTC-QLQ-C30 and items from the Brief Pain Inventory – Short Form, EORTC-QLQ-FA12 and Suppository Acceptance Questionnaire at each time point and changes from baseline will be summarized using descriptive statistics. Details of the scoring algorithms used to generate the QoL scores will be described in the SAP.

A Statistical Analysis Plan (SAP) will be developed and the analysis will be performed by a statistician using SAS {version TBD}.

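### Tolerability and suppository acceptance are analysed only in patients who completed a combination cycle, so early intolerance drops out of those two results

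*Combined protocol and SAP*

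**What the plan says.** Section 7.1 gives as a primary objective "To characterize the safety and tolerability of NOX66 alone and in combination with doxorubicin". Section 8.1.1 explains the lead-in in the same terms: "The purpose of the monotherapy treatment is to evaluate the safety and tolerability of NOX66 when administered alone".

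Section 14.2 defines two sets. The Safety Set takes everyone with at least one dose of idronoxil and is used for safety, toxicity and PK. The other set is defined thus: "All patients who complete at least one cycle of idronoxil + doxorubicin combination therapy will be included in the Full Analysis Set (FAS"). The sentence that follows is "Analyses of efficacy, tolerability, and biomarkers will be performed for this set". The synopsis has the same definition and the same assignment: "Analyses of efficacy, tolerability, and biomarkers will be performed for the FAS". Tolerability is not listed under the Safety Set in either place.

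Section 14.3.11 opens with "All Quality of Life (QoL) analyses will be performed on the FAS" and includes the Suppository Acceptance Questionnaire among the instruments summarised there. That questionnaire is scheduled for escalation patients on Monotherapy Day 7 (11.6.2.2), on Day 1 of Cycles 2 to 6, and at Cycle 6 Day 21 or Early Termination (11.6.2.9; Table 4, footnote 15).

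**The concern.** Membership of the FAS depends on having tolerated treatment well enough to finish a combination cycle. A tolerability result computed on that set is conditioned on the outcome it is meant to describe, and the error runs in one direction, in favour of the drug.

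In the lead-in the exclusion follows from the protocol's own rules as well as from dropout. Section 8.1.1 lets patients move on to combination therapy only if no DLT-equivalent toxicity has occurred. The synopsis and section 8.3.6 provide for replacing patients who do not tolerate monotherapy, up to 3 per dose level. A patient removed in this way can never enter the FAS.

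Suppository acceptance has the same problem. Someone who gives up because of the suppository is among the most informative respondents. The protocol schedules that person's answers and then leaves them out of the planned summary.

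**Working it through.** The plan states no figure for tolerability, so there is nothing to reproduce. The check is a comparison of texts, followed by arithmetic on assumed counts.

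**Texts side by side**

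- Objective (7.1) and purpose of the lead-in (8.1.1): tolerability of NOX66 alone, and in combination.
- Set used (14.2 and synopsis, in agreement): completers of at least one combination cycle.
- Set available but not used: the Safety Set, at least one dose of idronoxil.
- Any reassignment of tolerability or of the acceptance questionnaire elsewhere in section 14: none.

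**Formulae**

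Let N be the number treated, d the number who stop for intolerance before completing one combination cycle, and k the number who stop for intolerance later. Then

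- Safety Set rate = (d + k) / N
- FAS rate = k / (N − d)

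The d patients leave both numerator and denominator of the FAS rate. For NOX66 alone, k = 0 by definition, so the FAS rate is always 0%.

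**NOX66 alone, one dose level**

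Inputs from the documents: at most 3 lead-in replacements per dose level (8.3.6) and cohorts of 3 or 6 (14.1). Assumed: d patients stop in the lead-in for intolerance and are replaced, and the 3 or 6 others all complete Cycle 1.

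| d | Safety Set, 6 completers | Safety Set, 3 completers | FAS |
|---|---|---|---|
| 1 | 1/7 = 14.3% | 1/4 = 25.0% | 0% |
| 2 | 2/8 = 25.0% | 2/5 = 40.0% | 0% |
| 3 | 3/9 = 33.3% | 3/6 = 50.0% | 0% |

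**Combination, expansion cohort**

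Input from the documents: N = 16 (14.1). Assumed: d from 1 to 4, k of 0 or 2, and no replacement. No replacement fits section 8.3.6 if at least 12 patients still complete two cycles.

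| d | Safety Set, k = 0 | FAS, k = 0 | Safety Set, k = 2 | FAS, k = 2 |
|---|---|---|---|---|
| 1 | 1/16 = 6.3% | 0/15 = 0% | 3/16 = 18.8% | 2/15 = 13.3% |
| 2 | 2/16 = 12.5% | 0/14 = 0% | 4/16 = 25.0% | 2/14 = 14.3% |
| 3 | 3/16 = 18.8% | 0/13 = 0% | 5/16 = 31.3% | 2/13 = 15.4% |
| 4 | 4/16 = 25.0% | 0/12 = 0% | 6/16 = 37.5% | 2/12 = 16.7% |

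Replacement changes the figures but not the direction. If the four early stops in the last row were replaced by patients who did not stop for intolerance, the k = 2 rates would be 6/20 = 30.0% and 2/16 = 12.5%.

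**What stays outside the FAS restriction**

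- AE and SAE summaries, including separate ones for onset before the first doxorubicin dose and during Cycle 1 (14.3.4), with safety and toxicity on the Safety Set (14.2).
- Disposition (14.3.2) and exposure, including missed idronoxil doses and dose changes (14.3.3), for which no set is named.
- DLT and MTD evaluation, which keeps any patient with a Cycle 1 DLT (8.3.5).

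**The case against.** The best defence is that little depends on the word. The primary endpoints in 11.1.1 are safety parameters, and these are analysed on the Safety Set. The plan defines no tolerability endpoint or method. Early intolerance will still be visible in the lead-in and Cycle 1 AE summaries, in disposition, in exposure, and in the withdrawal reasons that 11.2.2 requires in the eCRF and the study report. All of this stands, and it limits the finding.

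It does not remove it. The population sentence is the only analysis rule the plan gives for tolerability, so a table produced under that name would follow it. The acceptance questionnaire is a concrete, scheduled analysis with an explicit FAS restriction.

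The documents do not support several stronger readings that a reader might infer:

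- *That the primary safety results, the MTD or escalation are biased.* They use the Safety Set or the evaluable-patient rule.
- *That the RP2D is biased.* Acceptability to patients is part of the RP2D wording in the synopsis and 8.3.6, but nothing says it will be judged from the FAS questionnaire summary. The questionnaire is listed as exploratory (11.1.2.4).
- *That everyone who stops in Cycle 1 is lost.* The plan does not define completing a cycle, and NOX66 is given on Days 1 to 7 of 21 only. A patient who took all Cycle 1 drug and stopped before Cycle 2 could be counted as a completer. Patients with dose holds who finish a cycle also stay in the FAS.
- *That the effect can be sized on all 34 planned patients.* Only escalation patients, up to 18 before replacements, receive monotherapy, and the synopsis says replacement takes the total above 34.

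**Conclusion.** The set assignment is wrong as written. Tolerability, part of a primary objective, and suppository acceptance are both restricted to patients selected for having tolerated a combination cycle.

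For NOX66 alone, discontinuation for intolerance is 0% on the FAS whatever happens; this needs no assumption. With 3 intolerant patients replaced at one dose level, the Safety Set rate would be 33% with 6 completers or 50% with 3. For the combination the gap depends on assumed counts and on how completion of a cycle is defined. In the expansion cohort, 1 to 4 early stops give 6.3% to 25.0% against 0% if nobody stops later for intolerance.

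The documents give no intolerance rate, so these figures show the mechanism and do not forecast its size. The bias is confined to results labelled tolerability and to suppository acceptance. It changes no test, sample size, DLT count or escalation rule. It should be fixed, but it does not undermine the primary safety analysis.

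**What to change.** In section 14.2, section 14.3.11, the synopsis and the SAP:

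1. Assign tolerability to the Safety Set and list its measures: discontinuation for intolerance, dose reductions, delays and missed doses.
2. Report by period: monotherapy among treated escalation patients, and combination among those who started it.
3. Summarise the Suppository Acceptance Questionnaire on the Safety Set, including Monotherapy Day 7 and Early Termination answers from patients who never completed Cycle 1.
4. State that the disposition and exposure summaries use the Safety Set.
5. Keep the FAS version of tolerability and acceptance as secondary, and say what completing a cycle means.

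The cost is wording. No further patients, visits or data are needed, and section 14.3.12 already calls for an SAP approved before the expansion cohort opens. The downside is that tolerability may look slightly worse.

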14.3 STATISTICAL METHODOLOGY

14.3.1 GENERAL STATISTICS METHODS

All data will be summarized by idronoxil dose group. For safety analyses, a summary group consisting of all dose groups combined may also be presented.

For all measurements, the baseline value will be the last measurement taken before the first dose of study drug, whether idronoxil or of idronoxil + doxorubicin depending on the cohort.

Standard summary statistics will be presented for all measurements. For continuous variables, the standard summary statistics will be the number of observations (n), mean, standard deviation, median, minimum and maximum. For categorical variables, the standard summary statistics will be the number and percentage of observations in each category. Categories that are specified on the eCRF which contain no observations will be presented in the data summaries with a value of 0.

An AE with a completely missing start date will be assumed to start one minute after the date-time of the first idronoxil dose. If the severity of a reported AE is missing, it will be assumed that the event is severe; similarly, if the relationship of a reported AE to study treatment is missing, it will be assumed that the event is definitely related to treatment. No other missing data will be imputed. Incomplete start dates for Adverse Events and Concomitant Medications and incomplete end dates for AEs will have missing parts imputed by a conservative procedure which will be specified in the Statistical Analysis Plan (SAP).

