11.4.2.3 Cardiac Monitoring

A 12-lead ECG after 5 minutes of rest in the supine position will be obtained at Screening. In the Dose Escalation Cohort, triplicate 12-lead ECGs in close succession at least 1 minute apart will be obtained after 5 minutes of rest in the supine position at -0.75, -0.5 and -0.25 hours prior to administration of NOX66 and at 1, 2, 5, and 8 hours after the first dose of NOX66 monotherapy (Day 1).

On Day 7 of Monotherapy, 12-lead ECGs will be recorded performed in triplicate in the same manner and time points as on Day 1. In addition, Holter monitoring, will be conducted from 8 to 24 hours post NOX66. On Day 2 of Cycle 1, the same evaluation will be done before and after administration of NOX66, and Holter monitoring will be performed from 8 to 24 hours after NOX66 administration (Dose Escalation and Dose Expansion Cohorts). On Day 2 of Cycles 2 to 6, (combination of NOX66 and doxorubicin), triplicate 12-lead ECGs will be obtained after 5 minutes of rest in the supine position at -0.25 hours prior to and at 1, 2, 5 and 8 hours post morning dose of NOX66.

On days when serial ECG readings occur, before electrodes are removed after the initial reading, the electrode position is to be marked on the skin with indelible ink and the same electrode position used for all subsequent ECGs for each patient.

The following windows are acceptable for performing the ECGs:

- +/-5 minutes for pre-dose ECGs required at -0.75, -0.5 and -0.25 hours prior to NOX66 administration.
- +/-10 minutes for post-dose ECGs required at 1 hour and 2 hours after NOX66 administration.
- +/-15 minutes for post-dose ECGs required at 5 hours and 8 hours after NOX66 administration.

Echocardiography will be assessed at the start of Cycles 3, 5 and at the end of Cycle 6 (or Early Termination), and compared to baseline (Screening).

If clinically indicated, an additional echocardiograph will be done at Cycle 1 prior to the first dose of doxorubicin. All clinically significant findings that are not present at baseline should be reported as AEs.

Echocardiogram assessment can be performed 1 day prior to the scheduled visit day.

For any patient with an absolute decrease in LVEF of >10% from the previous evaluation, or if the actual LVEF decreases to ≤40%, or ≥ Grade 3 LV systolic dysfunction, doxorubicin must be discontinued and echocardiograms are to be performed at 6-month intervals in the post treatment phase.

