14.3.7 ECG PARAMETERS

For each ECG parameter (PR, RR, QRS, and QT intervals, and QT interval corrected for heart rate using QTcF intervals where the QT intervals corrected for heart rate by Fridericia's formula [QTcF = QT/(RR)^{2/3}]), the parameter and the change from baseline in that parameter will be summarized at all time-points where an ECG is collected. Where triplicate ECG measurements are available, the descriptive statistics will be calculated using the arithmetic average of the three raw measurements. Holter monitoring will not assess ECG intervals but will provide information on cardiac rate and rhythms.

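### The general baseline rule, applied to ECGs, leaves six of nine pre-dose tracings unused in dose escalation and leaves dose expansion with one Screening ECG as baseline; a cheap improvement is available

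*Combined protocol and SAP*

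**What the plan says.** **Baseline rule.** Section 14.3.1 sets one rule for every measurement: "the baseline value will be the last measurement taken before the first dose of study drug". It adds that this dose is "whether idronoxil or of idronoxil + doxorubicin depending on the cohort".

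**ECG analysis.** Section 14.3.7 says that "the parameter and the change from baseline in that parameter will be summarized at all time-points where an ECG is collected". For triplicates, "the descriptive statistics will be calculated using the arithmetic average of the three raw measurements". It gives no ECG-specific baseline and does not mention combining the three pre-dose times.

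**Escalation schedule.** Section 11.4.2.3 calls for "triplicate 12-lead ECGs in close succession at least 1 minute apart", taken "at -0.75, -0.5 and -0.25 hours prior to administration of NOX66" on Monotherapy Day 1. That is 3 times x 3 tracings = 9 pre-dose tracings.

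**Expansion schedule.** NOX66 starts on Cycle 1 Day 1 (Sections 6.2 and 11.6.2.4). Table 4 with footnote 6 and Table 8 place the first post-Screening ECG on Cycle 1 Day 2. The only earlier one is at Screening: "A 12-lead ECG after 5 minutes of rest in the supine position will be obtained at Screening". It is not described as triplicate, and Section 11.6.1 allows it up to 28 days before Day 1.

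**The concern.** ECG parameters are among the primary safety endpoints, which Section 11.1.1 expresses as change from baseline. The protocol already spends effort on ECG noise through triplicates, supine rest and marked electrode positions on serial days. A noisy baseline gives some of that back, because its error enters every later change for the same patient.

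The two parts of the study differ:

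- **Escalation.** Readings that are already collected have no role in the baseline.
- **Expansion.** The readings are never scheduled before the first dose. The Cycle 1 Day 2 pre-dose triplicates follow a day of NOX66, so they cannot supply an untreated baseline.

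The cohort clause adds an ambiguity. If it means the combined dose on Cycle 1 Day 2, the expansion baseline is taken after NOX66 exposure. A NOX66 effect already present would then be subtracted out, which is bias and not noise.

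Section 14.3.1 also summarises by dose group. Unless the two parts are separated, which the synopsis allows but does not require, the MTD group of up to 6 + 16 = 22 patients would mix two kinds of baseline.

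**Working it through.** The documents state no SD or precision for QTcF, so there is no plan figure to reproduce. The SDs below are assumptions, shown as ranges.

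**Notation.** sr is the SD between replicates within a triplicate (assumed 4, 6 or 8 ms). st is the SD between time points within a day (3, 5 or 8 ms). sd is the day-to-day SD (0, 5 or 8 ms). One triplicate mean has within-day variance V = st² + sr²/3. Only measurement error is modelled, not true differences between patients.

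**1. Escalation, change within Monotherapy Day 1**

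- Last triplicate as baseline: V + V = 2V.
- Mean of all three triplicates: V + V/3 = 4V/3.
- SD ratio: sqrt(2 / (4/3)) = sqrt(1.5) = 1.22, whatever V is, if the pre-dose times are independent.
- With correlation rho among the pre-dose triplicates, and the post-dose value independent of them, the second variance is V + V(1 + 2rho)/3. The ratio is then sqrt(2 / (1 + (1 + 2rho)/3)):

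| rho | SD ratio | Inflation |
|---|---|---|
| 0 | 1.225 | 22% |
| 0.25 | 1.155 | 15% |
| 0.5 | 1.095 | 10% |
| 0.75 | 1.044 | 4% |
| 0.9 | 1.017 | 2% |

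In the independent case the SD of change falls from 5.4–13.1 ms to 4.4–10.7 ms over the assumed SDs.

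**2. Escalation, change to a later day**

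The day-to-day term enters both variances, so the ratio is sqrt((2V + 2sd²) / (4V/3 + 2sd²)). With independent time points it is 1.07–1.16 at sd = 5 and 1.03–1.11 at sd = 8. Example: sr = 4, st = 3 gives V = 9 + 16/3 = 14.33. At sd = 8 the ratio is sqrt((28.67 + 128) / (19.11 + 128)) = sqrt(156.67/147.11) = 1.03.

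**3. Expansion, change to Cycle 1 Day 2**

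- Single Screening ECG: V + st² + sr² + 2sd².
- Nine tracings on Cycle 1 Day 1: V + V/3 + 2sd².
- Six tracings on Cycle 1 Day 1: V + V/2 + 2sd².

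The term 2sd² stays in all three, because the serial post-dose ECGs start the day after a Day 1 baseline. The extremes over the assumed SDs are:

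| sr, st, sd (ms) | Variance: Screening | Nine | Six | SD ratio vs nine | SD ratio vs six |
|---|---|---|---|---|---|
| 4, 3, 8 | 167.33 | 147.11 | 149.50 | 1.07 | 1.06 |
| 8, 3, 0 | 103.33 | 40.44 | 45.50 | 1.60 | 1.51 |

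With the Screening ECG, the SD of change is 6.3–18.5 ms over the assumed SDs. These ratios treat time points within a day as independent apart from the day term. Correlation between them would shrink the gain.

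**The case against.** Five arguments stand against the point.

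- **The rule is generic.** Table 8 lists the three pre-dose times in one row, and Section 14.3.7 does not forbid pooling them. Section 14.3.12 defers data-handling rules to an SAP due before expansion opens. This stands in part: that SAP could define a pooled escalation baseline. It could not supply a Day 1 ECG that was never recorded in expansion.
- **The gain may be small.** Pre-dose times 15 minutes apart may be strongly correlated. This stands, and is why a range is given.
- **Little rests on it.** The ECG summaries are descriptive, with no test or sample size attached. The DLT criteria in Section 8.3.3 name no QTcF change, the synopsis trigger for extra ECGs is an absolute QTc of 500 ms, and concentration–QTc work is optional. This stands and sets the severity.
- **The remedy needs an amendment.** It affects several sections, not one sentence. This stands for the expansion part.
- **The remedy thins Day 2.** It removes tracings just before doxorubicin. This also stands, as a real trade-off.

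Three stronger readings are tempting but unsupported:

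- A reader might infer from 2V against 4V/3 that pooling is worth 50% more patients. That ignores between-patient differences in true change, which extra patients average over and extra baseline tracings do not.
- A reader might infer a threefold variance in expansion. That needs pure replicate noise (a single ECG of variance 3V, so 3V + V = 4V) set against nine tracings (4V/3). The proposed change yields six, and day-to-day variance remains.
- A reader might infer that expansion discards collected readings. It does not; none beyond Screening are scheduled before the first dose.

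**Conclusion.** The point holds as a cheap improvement of minor severity. On the text, the escalation ECG baseline is one triplicate out of three. The expansion baseline is either a single Screening ECG or, if the cohort clause means the combined dose, a value taken after a day of NOX66.

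Pooling lowers the measurement-error SD of same-day change for any correlation below 1 among the pre-dose times. The documents do not fix the size:

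- **Escalation:** 22% SD inflation at independence, 10% at correlation 0.5 and 2% at 0.9 for same-day changes. It is smaller for later days when there is day-to-day variation.
- **Expansion:** SD 1.07 to 1.60 times that from a nine-tracing Day 1 baseline, and 1.06 to 1.51 times that from the six tracings proposed. Both ranges rest on the assumed SDs and independent time points.

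Nothing here undermines the dose-escalation decisions or the validity of the safety summaries. What is affected is the precision of a descriptive primary safety measure in small groups and, under the second reading of the cohort clause, its interpretation in expansion.

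**What to change.** 1. **Sections 14.3.1 and 14.3.7.** Define ECG baseline as the mean of all tracings taken before the first NOX66 dose on the day of that dose. State that baseline precedes the first NOX66 dose in every cohort, which settles the cohort clause. For escalation this uses tracings already collected and costs only the wording.

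2. **Expansion schedule.** Move two of the three Cycle 1 Day 2 pre-dose triplicates to Cycle 1 Day 1, before the first NOX66 dose, and use the mean of those six tracings as baseline. Keep the -0.25 h triplicate on Day 2, matching the Table 8 layout for Cycles 2 to 6.

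**Cost.** The number of ECGs is unchanged, and Cycle 1 Day 1 is already a clinic visit with pre-dose procedures. The second change needs an amendment to the synopsis (Cardiac Monitoring), Sections 11.4.2.3 and 11.6.2.4, Table 4 with footnote 6, and Table 8, which would need separate columns by cohort. Section 17.7 requires IRB submission. The loss is six tracings just before doxorubicin on Day 2; the sponsor should confirm that the remaining triplicate is enough there. The change should be in place before expansion opens.

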14.3.4 ADVERSE EVENTS

An AE will be deemed treatment emergent (TEAE) if it starts or worsens in severity or toxicity after the beginning of treatment, whether with idronoxil or with idronoxil + doxorubicin.

Adverse events will be coded using the MedDRA Dictionary, Version 22.0 (or higher). Treatment emergent adverse events will be summarized by MedDRA Preferred Term and System Organ Classification for each dose group. Separate summaries will be provided for TEAEs with onset prior to the first dose of doxorubicin, with onset during the first cycle of idronoxil+ doxorubicin therapy, and for TEAEs with onset after the end of the first treatment cycle.

The toxicity of an AE will be assessed by the NCI-CTCAE, Version 5.0. Summaries of TEAEs will be provided by dose group and toxicity grade. Summaries of TEAEs will also be provided by dose group and Investigator-reported severity and by dose group and Investigator-reported relationship to study treatment.

A summary will be provided of the overall incidence and the incidence of component terms for the Standardized MedDRA Queries (SMQs) for Cardiac Failure and for Cardiomyopathy.

A separate summary will be provided of Serious Adverse Events (SAEs) by dose group. Summaries will be presented for all SAEs, for treatment-emergent SAEs, for treatment-emergent SAEs that occur prior to the first dose of doxorubicin, during the first cycle of idronoxil + doxorubicin combination treatment, and after the end of the first cycle of combination treatment.

Deaths on study or within 30 days after a patient exits the study will be summarized by treatment. A listing of all deaths will be provided.

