15.2.1.1 AE Reporting

All AEs are graded according to NCI-CTCAE v5.0. AEs are captured from the time of consent and must be reported in the eCRF.

. Some events may make the patient ineligible for enrollment. Unanticipated events should be reported to the IRB, according to its requirements. Patients will be questioned at every visit after the first dose until the last follow-up visit regarding the occurrence and nature of any TEAEs. All TEAEs will be reported, whether or not they are deemed to be related to investigational product.

A description of the event or diagnosis including dates, severity, relationship to the investigational product, action taken and outcome, and whether or not the event was also serious, must be reported on the AE eCRF for each TEAE recorded in the patient's chart.

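### Dating every undated adverse event to one minute after the first NOX66 dose is safe for the treatment-emergent flag but misallocates events in the onset-period summaries

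*Combined protocol and SAP*

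**What the plan says.** Section 14.3.1 gives one rule for all cohorts: "An AE with a completely missing start date will be assumed to start one minute after the date-time of the first idronoxil dose". It makes no exception for a known end date or reporting visit. Only incomplete dates are deferred to the SAP, so for wholly missing start dates the rule is final as written.

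The treatment-emergent definition in Section 14.3.4 is: "An AE will be deemed treatment emergent (TEAE) if it starts or worsens in severity or toxicity after the beginning of treatment". The same section plans separate summaries of "TEAEs with onset prior to the first dose of doxorubicin, with onset during the first cycle of idronoxil+ doxorubicin therapy", and a third "for TEAEs with onset after the end of the first treatment cycle". The SAE summaries follow the same split: "for treatment-emergent SAEs that occur prior to the first dose of doxorubicin, during the first cycle of idronoxil + doxorubicin combination treatment", and then after that cycle.

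On timing, Section 8.1.1 says of the escalation cohorts that "there will be 7 days of monotherapy treatment with NOX66 followed by a 5- day washout period prior to the start of combination cycles". Under Sections 6.2 and 8.1.2, expansion patients have no monotherapy period: NOX66 starts on Cycle 1 Day 1 and doxorubicin follows on Day 2. On collection, Section 15.2.1.1 says that "AEs are captured from the time of consent".

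**The concern.** A missing-date rule is conservative only in relation to a particular question. Placing an undated event just after the first dose ensures that it counts as treatment-emergent. The same imputed time then decides which onset-period summary receives the event, and there it works in one direction only. First NOX66 precedes first doxorubicin in both parts, so the event is always dated to before doxorubicin, whatever else is known about it.

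The split matters because the second primary objective (Section 7.1) covers the safety of NOX66 both by itself and with doxorubicin. These summaries are where the two can be told apart. An undated event that arose on the combination would be shown as arising before doxorubicin, and in most cases would be absent from the summary for the period in which it occurred. Section 14.3.1 also sets missing severity to severe and missing relationship to definitely related, so a poorly completed record could appear as a severe, definitely related event before doxorubicin.

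Separately, because collection starts at consent, an event that ended during screening but has no start date would be given an onset after its own end and would become a TEAE.

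**Working it through.** The plan gives no figure on this point, so there is nothing to reproduce. The check places the imputed time on each part's timeline.

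**Inputs** (days from first NOX66 dose)
- Imputed onset: 1 minute = 1/1440 day (Section 14.3.1).
- Start of Cycle 1: 7 + 5 = 12 in escalation (Section 8.1.1); 0 in expansion (Section 8.1.2).
- First doxorubicin: Cycle 1 Day 2, about 1 hour after NOX66 (Sections 8.1.1 and 11.6.2.4), so Cycle 1 start + 1 + 1/24.
- Cycle length 21 days; six cycles = 126 days.
- AE recording continues to 30 days after the last dose (Table 4, footnote 16). The last NOX66 dose is on Cycle 6 Day 7, so recording ends at Cycle 1 start + 5 × 21 + 7 + 30 = Cycle 1 start + 142.

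**Step 1: where the imputed onset falls**

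| | Escalation | Expansion |
|---|---|---|
| Cycle 1 | day 12 to 33 | day 0 to 21 |
| First doxorubicin | day 13.04 | day 1.04 |
| Before first doxorubicin? | yes | yes |
| Within Cycle 1? | no | yes |
| After Cycle 1? | no | no |

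The ±1 day window for Day 2 in Section 11.6.2 does not change this. Even if doxorubicin were given on the day of the first NOX66 dose, it would follow by about an hour, and the imputed onset is one minute.

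The table also shows an overlap in Section 14.3.4: Cycle 1 Day 1 lies both before first doxorubicin and inside Cycle 1. No rule says which summary takes an event on that day. This affects dated events in both parts, and every undated event in expansion.

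**Step 2: how often the period would be wrong**

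Assume uniform onset and six undelayed cycles.
- Share before doxorubicin, to the end of Cycle 6: escalation 13.04/(12 + 126) = 13.04/138 = 9.4%; expansion 1.04/126 = 0.8%.
- The same share to the end of AE recording: escalation 13.04/154 = 8.5%; expansion 1.04/142 = 0.7%.
- So about 91% of undated events in escalation and 99% in expansion would have begun on or after first doxorubicin, yet all are dated before it.
- Share after Cycle 1, a summary that no undated event can reach: escalation (138 − 33)/138 = 76%; expansion (126 − 21)/126 = 83%. If expansion events were assigned to the Cycle 1 summary instead, the period would still be wrong for that 83%.

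**Step 3: weight of one event**

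One patient is 1/3 = 33 percentage points in a group of 3, 1/6 = 17 in a group of 6, and 1/16 = 6 in the expansion cohort. The rate in the correct period falls by that amount only if the patient has no other dated event of the same term in that period.

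**The case against.** The strongest reply is that this will rarely arise. The rule covers only wholly missing start dates. Section 16.1.1 asks for time of onset, Section 15.2.1.1 requires dates on the AE form and questioning at every visit, Section 13.1 promises full source verification, and Section 13.2.2 adds programmed checks and queries. The plan gives no count of undated events. In addition, the overall summaries by dose group, grade, severity and relationship lose no event, and Section 14.3.12 leaves further data-handling rules to an SAP still to be approved. All of this stands and limits the size of the problem. It does not remove it, because the rule in Section 14.3.1 is already stated without exceptions.

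Two stronger readings are tempting, and the documents do not support them. A reader might infer that every undated event leaves the Cycle 1 summary. That is true in escalation only; in expansion (16 of up to 34 patients) the imputed time lies inside Cycle 1. A reader might also infer that the rule removes events from the DLT window and so biases the MTD. DLTs are judged at the end of Cycle 1 (Section 8.3.4) by the Safety Review Committee once the safety data are in (Section 8.1.1). Sites must notify a DLT at once (Section 15.2.2.3), and a DLT log is kept (Section 11.2). Nothing applies the imputation to that process.

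**Conclusion.** The point holds for the onset-period TEAE and SAE summaries. All undated events are dated to before doxorubicin, and none can appear after Cycle 1. In escalation none can appear in Cycle 1 either; in expansion they meet two overlapping definitions. The rule can also create a TEAE whose onset follows its end.

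Under uniform onset and six undelayed cycles, roughly nine in ten undated events in escalation and nearly all in expansion would be dated to before doxorubicin when they began after it. Those percentages describe undated events only, whose number is unknown and probably small. Dose-escalation decisions and overall TEAE counts are not at risk. This should be corrected because the split serves a primary objective and the groups are small enough for one event to show.

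**What to change.** 1. Use the imputed time only to set the treatment-emergent flag, and not when the end date or reporting visit shows that the event ended before the first dose.
2. For the onset-period summaries, place an undated event by the visit at which it was first reported and by its end date. For example, an event that ended before first doxorubicin belongs in the first window. Where these data do not settle the period, show the event in an *onset unknown* row.
3. Make the three windows in Section 14.3.4 mutually exclusive by stating which one takes events on Cycle 1 Day 1, for dated and undated events alike.

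No separate DLT-counting rule is needed. The cost is SAP wording and a few lines of programming. Section 17.3 allows changes to the planned analysis to be documented in the SAP, and Section 14.3.12 has the SAP approved before the expansion cohort opens.
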